Short Forearm Casting Versus Below-elbow Splinting for Acute Immobilization of Distal Radius Fractures

NCT02679066

November 13, 2015

JHM IRB - eForm A – Protocol

- **Use the section headings to write the JHM IRB eForm A, inserting the appropriate material in each. If a section is not applicable, leave heading in and insert N/A.**
- **When submitting JHM IRB eForm A (new or revised), enter the date submitted to the field at the top of JHM IRB eForm A.**

1. Abstract

- a. Provide no more than a one page research abstract briefly stating the problem, the research hypothesis, and the importance of the research.

Problem:

There is no consensus regarding the need to immobilize the elbow in immediate immobilization of closed distal radius fractures post-reduction. Decreased functionality of the upper extremity is a notable morbidity associated with below-elbow splinting of distal radius fractures post-reduction. Few studies have provided evidence comparing sugar tong splinting versus short-arm casting as methods of immediate post-reduction immobilization.

Research Hypothesis:

There is no significant difference in maintenance of reduction, changes in radiographic parameters, or functional scores at two weeks in patients with distal radius fractures treated acutely with a short arm cast versus a sugar tong splint.

Importance:

The study will provide guidance regarding the need for short forearm cast immobilization versus sugar tong splinting in early maintenance of reduction of closed distal radius fractures, as well as functional effects of sugar tong splinting versus short forearm casting.

2. Objectives (include all primary and secondary objectives)

To determine the success of sugar tong splinting versus short arm casting for maintenance of reduction of closed distal radius fractures and to compare the functional outcomes in patients treated with sugar tong splinting versus short forearm casting as guidance for immediate post-reduction immobilization of these fractures.

Primary objectives:

3. Background (briefly describe pre-clinical and clinical data, current experience with procedures, drug or device, and any other relevant information to justify the research)

- Koval et al. randomized patients to long-arm versus short-arm splinting of post-reduction closed distal radius fractures and reported comparable maintenance of reduction with better functional scores in patients immobilized in a short-arm splint and thus recommended this method for immediate post-reduction immobilization of closed distal radius fractures (Koval et al. 2006).
- Grafstein et al. randomized 101 adult patients with closed distal radius fractures to sugar tong splinting versus above-elbow circumferential casting versus above-elbow volar-dorsal splinting for immediate post-reduction immobilization and followed patients closely for 3 to 4 weeks. They reported no significant difference in loss of reduction, pain scores, range of motion, or ADLs between the three methods of immobilization and thus recommended treatment with any method with which the treating physician is most comfortable (Grafstein et al., 2010).
- Millet and Rushton randomized 99 women with closed distal radius fractures to below elbow plaster casts versus initial plaster casting followed by flexible casting to allow early joint range of motion and reported increased comfort, grip scores

and joint mobility in early treatment period without negative effects of early motion and thus concluded that early mobilization can be a beneficial treatment option (Millet and Rushton, 1995).

- Pool prospectively studied range of motion and radiographic parameters over a two year period in over 200 patients with Colles' fractures treated with five different combinations of above- and below-elbow immobilization and concluded that while all patients went onto union and adequate function, those immobilized in above-elbow plaster lost some degree of supination. He found no benefit to above-elbow immobilization and recommended only below-elbow post-reduction immobilization (Pool, 1973).
- Sarmiento reviewed a case series of 44 patients with intra-articular distal radius fractures treated initially with an above-elbow cast initially and transitioned early to a brace allowing elbow and wrist range of motion while restricting pronation-supination and concluded that although fracture collapse did occur, functional results were good and the early mobilization reduced the stiffness and incapacitation associated with treatment of distal radius fractures (Sarmiento et al.)

4. Study Procedures

- a. Study design, including the sequence and timing of study procedures (distinguish research procedures from those that are part of routine care).
 - b. Study duration and number of study visits required of research participants.
 - c. Blinding, including justification for blinding or not blinding the trial, if applicable.
 - d. Justification of why participants will not receive routine care or will have current therapy stopped.
 - e. Justification for inclusion of a placebo or non-treatment group.
 - f. Definition of treatment failure or participant removal criteria.
 - g. Description of what happens to participants receiving therapy when study ends or if a participant's participation in the study ends prematurely.
- Prospective, randomized, controlled trial
 - One hundred twenty adult patients with closed fractures of the distal radius will be randomized to below-elbow, sugar-tong splinting versus short arm casting for immediate post-reduction immobilization.
 - Residents will undergo a teaching session specifically for instruction on sugar tong splinting versus short arm casting. On-call resident will have access to an electronic folder containing randomization of patient to sugar tong splint versus bivalved short arm cast. All reductions will be performed under local hematoma block with 1% lidocaine and traction and less than three attempts at reduction.
 - Patients will follow up at one, two and four weeks for repeat AP and lateral radiographs of the forearm to measure radiographic parameters to determine maintenance of reduction and will complete the Disabilities of the Arm, Shoulder and Hand Score (DASH) for functional scoring of the upper extremity at two weeks.
 - Maintenance of reduction, as defined below, will be compared between splint constructs overall and in stable versus unstable fractures in each immobilization group. Specific changes in radial height, radial inclination and volar tilt as continuous variables will also be compared, as will DASH scores measuring functionality.
 - Maintenance of reduction will be defined as: loss of reduction of < 2 mm radial height, < 5 degrees of radial inclination or < 10 degrees of volar tilt and/or < 2 mm intra-articular step off, in follow up radiographs as compared to immediate post-reduction radiographs (Koval et al., 2006).
 - Unstable fractures will be defined as, at injury: > 4 mm radial shortening, > 10 degrees dorsal tilt, radial-ulnar translation of radius > 2 mm, dorsal comminution > 50% diameter of radius, > 2mm intra-articular displacement (Koval et al., 2006; Stoffelen and Broos, 1998). Fractures meeting these criteria will undergo ORIF after reduction and at a later time. However, reduction parameters and maintenance of reduction will be evaluated and compared for both splinting techniques until ORIF.

5. Inclusion/Exclusion Criteria

- Inclusion criteria: adult > 18 years of age, closed fracture, isolated injury, no prior injury to ipsilateral forearm, less than or equal to two attempts at reduction.

6. Drugs/ Substances/ Devices

- a. The rationale for choosing the drug and dose or for choosing the device to be used.
- b. Justification and safety information if FDA approved drugs will be administered for non-FDA approved indications or if doses or routes of administration or participant populations are changed.

- c. Justification and safety information if non-FDA approved drugs without an IND will be administered.

Not Applicable

7. Study Statistics

- a. Primary outcome variable.
- b. Secondary outcome variables.
- c. Statistical plan including sample size justification and interim data analysis.
- d. Early stopping rules.

Primary outcome variable: Maintenance of reduction

Secondary outcome variables: Radiographic parameters analyzed individually: radial height, radial inclination, volar tilt, DASH scores

Statistical plan including sample size: Sample size was calculated based on standard deviations for the above-noted outcomes variables reported in the literature and selected a sample size based on the largest calculated sample size. This was increased from 167 to 200 to account for expected dropout.

Early stopping rules: Less than 50% patient follow-up.

8. Risks

- a. Medical risks, listing all procedures, their major and minor risks and expected frequency.
- b. Steps taken to minimize the risks.
- c. Plan for reporting unanticipated problems or study deviations.
- d. Legal risks such as the risks that would be associated with breach of confidentiality.
- e. Financial risks to the participants.
 - No medical risks outside of standard of care.
 - Patients will be treated with standard of care.
 - Research committee of Department of Orthopaedic Surgery follows the progress of the project.
 - No legal risks.
 - No financial risks.

9. Benefits

- a. Description of the probable benefits for the participant and for society.

Below-elbow splinting is associated with decreased morbidity

10. Payment and Remuneration

- a. Detail compensation for participants including possible total compensation, proposed bonus, and any proposed reductions or penalties for not completing the protocol.

Not Applicable

11. Costs

- a. Detail costs of study procedure(s) or drug (s) or substance(s) to participants and identify who will pay for them.

Not Applicable

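### The research hypothesis is worded as no significant difference and no rule says how a non-significant result is read, so such a result would satisfy it without showing that cast and splint are comparable

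*Combined protocol and SAP*

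**What the plan says.** - Section 1, Research Hypothesis: "There is no significant difference in maintenance of reduction, changes in radiographic parameters, or functional scores at two weeks", for short arm cast versus sugar tong splint.
- Section 1, Importance: "The study will provide guidance regarding the need for short forearm cast immobilization versus sugar tong splinting".
- Section 2 gives a neutral aim: to determine how well each method holds the reduction and to compare function. It presupposes no result.
- Section 3, on a cited three-arm trial: "They reported no significant difference in loss of reduction, pain scores, range of motion, or ADLs between the three methods of immobilization". The protocol then reports, without comment, that trial's advice to use whichever method the physician prefers.
- Section 4: "Maintenance of reduction, as defined below, will be compared between splint constructs overall and in stable versus unstable fractures in each immobilization group". On timing: "Patients will follow up at one, two and four weeks for repeat AP and lateral radiographs of the forearm". On numbers: "One hundred twenty adult patients with closed fractures of the distal radius will be randomized".
- Section 7: "Primary outcome variable: Maintenance of reduction". On sample size: "This was increased from 167 to 200 to account for expected dropout".

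No section names a test, a significance level, a confidence interval, a margin for the between-arm difference, or a rule for reading a non-significant result. The millimetre and degree limits in Section 4 classify each patient as having kept or lost reduction. They are not a margin for the difference between arms.

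**The concern.** The statement labelled as the research hypothesis is one that a significance test can only fail to reject. Read literally, the trial's hypothesis is met whenever the test is non-significant, including when the data are too sparse to say anything. Failing to detect a difference is not evidence that the difference is small.

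The result is meant to guide the choice of immobilization. Without a reading rule, a result compatible with a clinically large excess of lost reductions on one method could be written up as confirming the hypothesis. The Background shows how easily this happens, since it passes on one trial's non-significant result together with the recommendation drawn from it.

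**Working it through.** **What can be reproduced.** The base figure of 167 cannot be reproduced, because Section 7 gives no significance level, power, standard deviation, difference or event rate. Only the inflation can be checked: 167/200 = 0.835, which implies 16.5% dropout. The figures below therefore illustrate how uninformative a non-significant result could be. They do not test the sample size.

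**Inputs.** From the documents: 120 patients (Section 4) and 167 before inflation (Section 7). Assumed: 1:1 allocation, two-sided 5%, all patients evaluable, 167 read as a total, and the loss rates shown. That gives n = 60 or 83.5 per arm.

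**Step 1: one possible result.** Suppose 12/60 lose reduction in one arm and 21/60 in the other (20% versus 35%).
- Difference d = 0.35 - 0.20 = 0.15.
- Pooled rate = 33/120 = 0.275. Pooled SE = sqrt(0.275 × 0.725 × 2/60) = 0.0815. z = 0.15/0.0815 = 1.84, p = 0.066.
- Unpooled SE = sqrt((0.20 × 0.80 + 0.35 × 0.65)/60) = 0.0804. 95% CI = 0.15 ± 1.96 × 0.0804, or -0.8 to +30.8 points.

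This result satisfies the hypothesis as worded, yet it does not exclude a 30-point excess. It was chosen at the edge of significance: with one more event in the worse arm, 12/60 versus 22/60 gives p = 0.043.

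**Step 2: how often a real difference would be non-significant.** With pooled SE se0 and unpooled SE se1, the chance of p > 0.05 is 1 - Φ((d - 1.96 × se0)/se1). For 20% versus 35% with 60 per arm: (0.15 - 1.96 × 0.0815)/0.0804 = -0.12, so the chance is 0.548.

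| True loss rates | Excess | 120 in total | 167 in total |
|---|---|---|---|
| 5% v 20% | 15 points | 0.295 | 0.159 |
| 10% v 25% | 15 points | 0.418 | 0.273 |
| 20% v 35% | 15 points | 0.548 | 0.415 |
| 30% v 45% | 15 points | 0.605 | 0.483 |
| 20% v 45% | 25 points | 0.159 | 0.061 |
| 30% v 55% | 25 points | 0.201 | 0.088 |

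Section 7 does not say whether 167 is a total or per arm. If it were per arm, the two 15-point rows at 20-30% base loss would fall to 0.130 and 0.189.

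**Step 3: what does not depend on these assumptions.** The gap between the wording and what a non-significant test can show exists at any N and any loss rate. The assumptions affect only its size.

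**The case against.** The sentence may be no more than a conventional null hypothesis entered in a form field. Section 2 is neutral, Section 4 says only that outcomes will be compared, and a detected difference would give guidance too. Nothing forbids confidence intervals, and the error could still be avoided when the results are written up. The loss rates are assumed, the worked example is near the worst case among non-significant results, and a 25-point difference would usually be detected.

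Much of this stands, and it limits the point to one of wording and reporting. It does not remove the point: the protocol labels the null as its research hypothesis, offers the result as guidance, and supplies no rule that separates a comparable result from an inconclusive one.

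Three stronger readings are tempting, and the documents support none of them.
- A reader might infer that the trial plans to declare equivalence when p > 0.05. No section says so, and no significance level is given.
- A reader might infer that a margin is required. No formal equivalence or non-inferiority claim is made, so it is not.
- A reader might infer that the trial is too small. No target difference is stated against which that could be judged. The conflict between 120 and 200 patients must be reconciled, but it is a separate finding.

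**Conclusion.** The point holds as a defect of wording and interpretation and should be fixed. As written, a non-significant comparison meets the research hypothesis without showing that cast and splint are comparable.

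Under the stated assumptions, a true 15-point excess at 20-30% base loss would go undetected in about 55-60% of trials with 120 patients and 42-48% with 167 in total. At 5-10% base loss the figures fall to about 30-42% and 16-27%. A true 25-point excess at 20-30% base loss would be missed in about 16-20% and 6-9%. How much this matters in practice depends on loss rates and a final N that the documents do not settle.

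**What to change.** Replace the Research Hypothesis with an estimation aim and add one sentence on interpretation, for example:

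> The primary analysis will estimate the difference in the proportion maintaining reduction (cast minus splint) at [the one primary time point], with a two-sided 95% confidence interval. A non-significant p-value alone will be reported as inconclusive and not as evidence that the methods are comparable.

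The sponsor must name the primary time point among the one-, two- and four-week radiographs. The mention of two weeks in the hypothesis does not settle it, because it may apply only to the functional scores. Report the radiographic parameters and DASH as secondary estimates with 95% confidence intervals.

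**Cost.** Wording and reporting only, with no extra patients, visits or measurements. The downside is that a non-significant result can no longer be presented as confirming the hypothesis, so the trial may have to be reported as inconclusive.

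**Limit.** This change prevents a false claim of comparability but gives no route to a valid one. A positive claim would need a margin, clinically justified and fixed before any outcome comparison. That is a trade-off for the sponsor, because a useful margin may be out of reach at this N, and it is not part of the required change.

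### Section 4 randomises 120 patients, section 7 calculates 167 and raises it to 200 for dropout; no reading reconciles them and nothing says which governs.

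*Combined protocol and SAP*

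**What the plan says.** Section 4 (Study Procedures) gives the enrolment in its design description: "One hundred twenty adult patients with closed fractures of the distal radius will be randomized", to either splint or cast. It does not say whether this is a total or a per-arm number, but one number divided between two treatments is naturally a total.

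Section 7 (Study Statistics) gives a different size. On the basis of the calculation it says: "Sample size was calculated based on standard deviations for the above-noted outcomes variables reported in the literature". On the choice among the results it says the investigators "selected a sample size based on the largest calculated sample size". It then adds: "This was increased from 167 to 200 to account for expected dropout". It does not say whether 167 and 200 are totals or per arm, what dropout rate was expected, or which outcome produced 167. The same section names the primary outcome: "Primary outcome variable: Maintenance of reduction".

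No other part of the document mentions 120, 167 or 200 as a sample size. There is no amendment history, and no redaction is visible at either place.

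**The concern.** The number to be randomised is a basic design parameter, and here it has two values. A team following section 4 stops at 120; a team following section 7 stops at 200. The one early stopping rule in section 7 concerns the follow-up rate and does not settle the target. Without a single target fixed in advance, the decision on when to stop recruiting can be questioned later.

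If 200 is the true target, section 4 understates enrolment by 80 patients (both figures read as totals). If 120 is the true target, the calculation in section 7 does not describe this trial, and the trial will be less precise than that calculation requires.

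The hypothesis in section 1 makes this matter more. It is framed as an absence of significant difference between the two methods. If a real difference exists, a smaller trial is more likely to miss it, and so to return the result that the hypothesis predicts.

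**Working it through.** **Inputs.** 120 randomised (section 4); 167 calculated and 200 after allowance for dropout (section 7). Alpha, sidedness, power, effect size or margin, standard deviations, event rates, allocation ratio and dropout rate are not stated.

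**The plan's own figures.** 167 cannot be reproduced, because none of its inputs is given. The step from 167 to 200 can be checked and is coherent:
- Dividing by the retained fraction: 1 − 167/200 = 16.5% loss.
- Multiplying up: 200/167 − 1 = 19.8%, close to a 20% mark-up (167 × 1.20 = 200.4).
- A true 20% loss would need 167/0.80 = 208.75, so 209 patients, which is not the figure given.

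**Does any reading reconcile the two sections?**

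| Section 4 read as | Section 7 read as | Comparison |
|---|---|---|
| total (120) | total (167, 200) | 1 − 120/167 = 28% below; 1 − 120/200 = 40% below |
| total (120) | per arm (334, 400) | 1 − 120/334 = 64% below; 1 − 120/400 = 70% below |
| per arm (240) | total (167, 200) | 240/167 = 1.44, so 44% above; 240/200 = 1.20, so 20% above |
| per arm (240) | per arm (334, 400) | 28% and 40% below, as in the first row |

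None agrees. Nor can 120 be the number expected to complete out of a larger enrolment: section 4 says these patients are randomised, and section 7 puts the number needed before dropout at 167.

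**Patients with data if 120 are randomised.** At the implied loss, 120 × 167/200 = 100.2, about 100. If instead a true 20% loss was expected, 120 × 0.80 = 96.

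**Precision.** Section 7 rests on standard deviations, so take a difference in means with the same standard deviation and allocation. Confidence interval width is then proportional to 1/√n, and the width relative to the planned one is √(167/n), with 167 as a total:
- n = 120: √(167/120) = 1.18, 18% wider.
- n = 100: √(167/100) = 1.29, 29% wider.
- n = 96: √(167/96) = 1.32, 32% wider.

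This needs no assumed alpha, power or type of test. If 167 is per arm, the ratios become √(334/120) = 1.67 and √(334/100) = 1.83.

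**Power, as illustration only.** Assume a two-sided 5% superiority test of means, with 167 in total giving 80% or 90% power. Then power(n) = Φ((1.960 + z) × √(n/167) − 1.960), with z = 0.842 or 1.282:
- n = 120: 66% (80% design) or 78% (90% design).
- n = 100: 58% or 71%.

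**The case against.** The strongest reply accepts the contradiction but disputes its consequences.

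- **The driving outcome is unnamed.** 167 is the largest of several calculated sizes, so it is what one unidentified outcome needs. The size needed for maintenance of reduction is unknown and might be 120 or less. This stands. The loss of precision is shown only for the outcome that set 167, and a formula for means does not carry over directly to a maintained-or-lost endpoint.
- **Section 4 never says its figure is a total.** If 120 were per arm and section 7's figures were totals, section 4 would exceed 200 and the direction would reverse. This is also fair: the shortfall of 80 depends on the total reading. The conflict remains, since 240 is neither 167 nor 200.
- **The per-arm figures for section 7 enlarge the gap on a reading the document does not state.** Agreed. The documented gap is 120 against 167 and 200; the larger figures are conditional.
- **The dropout rate is inferred.** Also agreed. A range of about 96 to 100 patients with data is fairer than one number.
- **The power figures rest on assumed inputs, and superiority is only one possible frame.** Agreed. They show scale only, and the conclusion does not depend on them.

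None of these removes the inconsistency or shows which figure is operative.

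**Conclusion.** The concern holds and must be fixed. Sections 4 and 7 give sample sizes for the same trial that cannot both be right, and the document does not show which applies. On the natural reading as totals, the randomised number is 28% below the calculated requirement and 40% below the requirement with dropout, a difference of 80 patients.

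That conclusion rests only on the stated numbers. The precision cost of 18% to 29% (32% if a true 20% is lost) further assumes that 167 is a total, that the outcome driving it is a difference in means, and that the standard deviation is unchanged. The effect on the primary outcome cannot be quantified from the document.

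**What to change.** Give one enrolment figure in sections 4 and 7, say whether it is a total or per arm, and say the same of 167.

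- **If 200 in total is the plan:** correct the number in section 4. This changes one phrase, and recruitment is 80 above the present section 4 figure. If 200 proves to be per arm, the total is 400, which is 280 above it.
- **If 120 is the plan:** replace the 167-to-200 statement in section 7 with 120 and the number expected to have data (about 100 at the 16.5% loss implied by 167/200). Restate the power or detectable difference at that size for a named outcome, and give it for maintenance of reduction too. This costs one sentence and one recalculation, with no extra patients, but the stated power or detectable difference will be less favourable.

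In either case, stating the expected dropout rate would remove the ambiguity between 16.5% and 20%.

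### Allocation runs through a folder open to the on-call resident, and nothing in the plan prevents the arm being known before enrolment or reduction

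*Combined protocol and SAP*

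**What the plan says.** All of this is in the combined protocol and SAP.

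- **Allocation (Section 4).** The delivery of the assignment is described once: "On-call resident will have access to an electronic folder containing randomization of patient to sugar tong splint versus bivalved short arm cast".
- **Who handles it (Section 4).** The sentence just before reads: "Residents will undergo a teaching session specifically for instruction on sugar tong splinting versus short arm casting". The text does not say who enrols patients or who performs the reduction.
- **What is compared (Section 4).** Patients "will be randomized to below-elbow, sugar-tong splinting versus short arm casting for immediate post-reduction immobilization".
- **Timing (Section 4, item a).** The form asks for "Study design, including the sequence and timing of study procedures". The answer gives follow-up visits at one, two and four weeks, but no time at which the assignment is seen.
- **Outcome (Sections 7 and 4).** "Primary outcome variable: Maintenance of reduction". It is judged "in follow up radiographs as compared to immediate post-reduction radiographs".
- **Reduction and eligibility (Sections 4 and 5).** "All reductions will be performed under local hematoma block with 1% lidocaine and traction and less than three attempts at reduction". The inclusion criteria also list "less than or equal to two attempts at reduction".

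**The concern.** Randomisation protects the comparison only if nobody who decides on enrolment, or on care before the assigned treatment starts, can know the arm in advance. Here the one stated mechanism gives access to a clinician on call, with no stated barrier.

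Two things could be affected. The first is who is enrolled: a patient with a difficult fracture might be entered or passed over according to the arm expected. The second is the reduction itself, if its effort or technique varied with the construct to follow. The second route matters in this trial because the reduction sets the reference film for the primary outcome. In either case the arms could differ for reasons other than cast or splint.

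**Working it through.** The plan gives no figure on this point, so there is nothing to reproduce. The check is a reading of the whole document for the elements that concealment needs.

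| Element | What the document says |
|---|---|
| Who generates and holds the sequence | Not stated |
| Folder shows one assignment or a list | Not stated; the wording fits either |
| Upcoming assignments hidden | Not stated |
| Eligibility and enrolment logged before an assignment is seen | Not stated |
| Opening of an assignment time-stamped | Not stated |
| Reveal placed before or after the reduction | Not stated |
| Baseline film taken before or after the cast or splint is applied | Not stated |

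Consent pages were removed from the text supplied for review, so a missing consent step is not counted. Nothing looks cut or redacted in the allocation sentence itself.

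**Does other wording supply the timing?** The reference to immobilisation after reduction in "will be randomized to below-elbow, sugar-tong splinting versus short arm casting for immediate post-reduction immobilization" names the treatments compared. It fixes when the construct is applied, not when the assignment is read. The form's prompt on sequence and timing is not answered on this point.

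**Is the resident a treating clinician?** This is an inference. Residents are taught both constructs, and the next sentence gives the on-call resident the assignment, which is most naturally needed by the person applying the construct. Control over enrolment is a further inference.

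**Does the reveal touch the outcome?** Maintenance of reduction is a change from the post-reduction films. If the arm is known before the reduction, the reference point is created with the arm known.

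**Does it touch eligibility?** For whole attempts, fewer than three (Section 4) and at most two (Section 5) are the same limit. Because it is also an inclusion criterion, eligibility is settled only once the reduction is done. This is a secondary route, since the same limit already applies as a procedure.

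**Illustration of the enrolment route, on assumed values only.** Suppose there is no true difference, half of patients have a poor prognosis, and loss of reduction is 50% in them and 20% in the rest. Suppose a share s of poor-prognosis patients is not enrolled when one particular arm is next.

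- Expected loss in the unaffected arm: 0.5 × 0.20 + 0.5 × 0.50 = 0.35.
- Expected loss in the affected arm: [0.5 × 0.20 + 0.5 × 0.50 × (1 − s)] / [0.5 + 0.5 × (1 − s)].
- s = 0.10: 0.325 / 0.95 = 0.342, a false difference of 0.8 percentage points.
- s = 0.50: 0.225 / 0.75 = 0.300, a false difference of 5.0 percentage points.

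The rejection rate of a two-sided 5% test is 1 − Φ(1.96 − d/SE) + Φ(−1.96 − d/SE), where d is the false difference and SE = √[a(1 − a)/n + b(1 − b)/n], with a and b the two expected proportions and n the number per arm. For s from 0.10 to 0.50 it runs from 5.1% to 9.0% with 60 per arm, and from 5.2% to 11.8% with 100 per arm. These arm sizes are half of the 120 in Section 4 and half of the 200 in Section 7, assuming equal allocation. None of the prognosis or selection inputs comes from the document, so this shows how the route works and does not estimate bias in this trial.

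**The case against.** **The folder may be safe in practice.** The sentence speaks of the randomisation of a patient, in the singular. It could describe a folder that gives an identified patient's assignment only once that patient is in the study. On that reading the arm could not be known before enrolment. This is fair, and it rules out saying that the arm can be known early under every reading. But the plan does not state that restriction, and even this reading leaves the reveal free to come before the reduction.

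**A reader might infer an open list of future assignments.** The document does not support that. It neither describes such a list nor shows a decision to leave assignments visible. The defect is an absent safeguard.

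**The resident's role is inferred, and some enrolment steps may have stood on removed pages.** Both points stand as limits. The firmer ground is the missing one-at-a-time release and the missing timing relative to the reduction, neither of which depends on the consent pages.

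**Reductions are standardised, and loss is measured from each patient's own film.** Standardised anaesthesia, traction and number of attempts narrow the reduction route but do not close it. A different starting point need not produce a different loss, nor shift every radiographic component. The effect is therefore possible, not shown.

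**Imbalance could be adjusted for.** In part: stable or unstable status is defined at injury, and a comparison by it is already planned. Selection on unmeasured features could not be reliably removed by analysis.

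**Treatment cannot be masked here anyway.** Masking after application is a different matter. Concealment before assignment is feasible in an open-label trial.

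**Conclusion.** The point holds as a missing safeguard on the primary comparison. Followed exactly, the stated mechanism does not prevent the on-call resident from knowing the arm before the patient is enrolled or reduced. This rests on the document's silence about release and timing, and on the inference that the resident is a treating clinician; the enrolment route also assumes some say over who is entered.

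The size and direction of any bias cannot be derived. A reader might infer that the comparison is already biased, or biased towards one construct. The document supports neither. The change should be made because the gap bears on the primary outcome and is cheap to close. Confidence is medium.

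**What to change.** Replace the folder sentence in Section 4 with text along these lines:

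*Assignments are held in sequential locked files or a database randomisation module. One time-stamped assignment is released at a time, after enrolment and the protocol's own eligibility criteria have been logged and the reduction is complete, at the point of immobilisation. The resident has no view of upcoming assignments.*

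Add a sentence stating whether the baseline radiograph is taken before or after release. If it is taken after, the reduction is protected but the reference film is still obtained with the arm known, and the reader should be told so.

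The change concerns only when and how the assignment is seen. It sets no condition on the reduction, the attempts limit or imaging. The cost is setting up the locked files or module, one paragraph of protocol text, and one extra logging step before immobilisation. No visits are added.
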